#### Control - standard care

Patients will be prescribed antibiotics according to the local antibiotic prescribing guidelines and using standard microbiology sampling, culture and sensitivity testing. Best practice including daily review of antibiotics, in consultation with microbiology teams, is encouraged. Local teams are advised to both de-escalate antibiotic therapy and prescribe short courses of antibiotics, as clinically appropriate, as recommended by Public Health England.(42)

Sponsor: Imperial College London

Version 1.1 22-Aug-2023

#### Fluid trial

Intervention – Conservative fluid therapy with de-resuscitation

A conservative fluid strategy will be followed as soon as possible after randomisation. Once initial early hypovolaemia has been corrected and in the absence of suspected or overt bleeding, or other fluid loss, a 250ml bolus of an isotonic crystalloid may be given if any of the following objective signs of possible hypovolaemia are present:

- Skin mottling beyond the area of the kneecap
- Blood pressure target cannot be maintained despite up-titration of noradrenaline or other vasoactive drugs
- Serum lactate ≥3 mmol/L
- Urine output < 0.25 ml/kg/h (on Day 1 only)

After administration of any fluid bolus, the patient should be re-assessed.

Further fluid boluses may be given if, on re-assessment, signs of possible hypovolaemia remain. No maximum volume of fluid boluses is specified. However, if there is no improvement after such fluid boluses, (for example after four boluses, 1000mL), the likelihood of benefit from further fluid boluses is very low and should not be given.

No routine (maintenance) intravenous fluid will be given other than to correct electrolyte abnormalities or to prevent ketosis, although replacement of bleeding or measured external fluid losses (e.g. vomiting, nasogastric losses, drain fluid) of more than 0.5 litre/day may be given in a 1:1 ratio. Normal feeding will continue as per local ICU protocol. Intravenous drugs will be given in the smallest acceptable volumes.

On a daily basis (days 2-5), patients will be assessed for cardiovascular stability. If stable (defined as a norepinephrine requirement <0.2 µg/kg/min or equivalent and not increasing, with no signs of possible hypovolaemia as described above) AND with signs of fluid overload (defined as >3000 ml cumulative positive fluid balance from ICU admission or oedema in more than one site [arms, legs, flanks, abdominal wall, chest x-ray]), then de-resuscitation will be given.

Deresuscitation will consist of combination diuretic therapy (oral indapamide\* 5mg daily, and furosemide 0.25mg/kg IV bolus (to the nearest 10mg, maximum 40mg) followed by an infusion starting at 5mg/hr, titrated between 2-20mg/hr to aim for at least a negative fluid balance of ~1000 ml/day.

\* Or any equivalent thiazide diuretic e.g. metolazone 5mg OD / bendroflumethiazide 5mg OD

Note, if there is excessive diuresis resulting in a larger negative balance or that the patient develops cardiovascularly instability the furosemide infusion should be reduced or stopped.

Patients requiring renal replacement therapy will not receive diuretics but the clinicians will target a similar negative balance through fluid removal.

There will be daily re-assessment according to previous criteria (oedema, fluid balance, cardiovascular stability). Once the patient is no longer assessed to be fluid overloaded (neutral fluid balance and/or no oedema), de-resuscitation will stop.

Sponsor: Imperial College London

Version 1.1 22-Aug-2023

If eligibility criteria for deresuscitation are not met, diuretics should not be given and the patient should be reassessed the following day.

The conservative fluid therapy with de-resuscitation will continue until day 5 or the patient is discharged from ICU, whichever comes first.

See Appendix 1 for a treatment flowchart

Control - standard care

Patients will be prescribed fluids according to usual care, at the discretion of the treating clinicians. Intravenous drugs will be given in standard dilutions according to local ICU policy and maintenance fluid will be allowed if deemed required by the treating clinician. Fluid boluses will be given as deemed clinically indicated and sites will be encouraged to follow the Best Practice Statement in the Surviving Sepsis Campaign international guidelines that "fluid administration is continued as long as hemodynamic factors continue to improve... [applying] a fluid challenge technique".(2)

Fluid balance targets will be set by the treating clinicians and diuretic use will be allowed as clinically indicated.

#### 5.6.3 GM-CSF

Intervention / control – GM-CSF (sargramostim) / placebo

In the subset of patients requiring mechanical ventilation, or with two or more organ failures and with persistent lymphopaenia (defined as an absolute lymphocyte count <1.2 x10^9/L on two consecutive calendar days at least 12 hours apart, with no values >1.2 x10^9/L in between) subcutaneous GM-CSF (sargramostim) or a matching placebo will be given.

The dose will be 500µg (two vials) for patients ≥50kg, and 250µg (one vial) for patients <50kg, once a day for 8 days in the ICU.

If the patient is discharged from the ICU before the 8th day then the study drug should be given on the ward until 8 doses in total have been, if logistics allow. It will not be a protocol deviation if this is not possible. If the patient is discharged hospital before the 8th day then the study drug will stop.

#### Follow-up

Patients will be followed up by the clinical research team daily whilst in ICU.

Once the patients have left ICU and been discharged to the general ward, they will be followed up prior to hospital discharge and at 90 days and 6 months. Follow-up at 1 year will be via medical records and data linkage with NHS records wherever possible.

# **Laboratory Evaluations**

#### **Blood tests**

10ml of additional blood will be collected on inclusion into the trial and sent to a central lab for PCR-based pathogen testing.

Sponsor: Imperial College London

Version 1.1 22-Aug-2023

Routinely collected clinical blood samples will be used to measure procalcitonin and absolute lymphocyte count measurement in local clinical laboratories at the recruiting hospital.

# **Exploratory / Research samples**

In addition, 20ml of blood will be collected on inclusion and sent to a central lab for storage of DNA, RNA and serum in the Imperial Tissue Bank for analysis in other ethically approved studies. For patients in the GM-CSF trial three additional 7ml of blood samples for RNA storage will be collect on inclusion and days 3 and 5 after randomisation. If resources prevent collection of the exploratory / research samples this is not a protocol deviation.

# Sample storage and analysis

The blood samples for PCR-based pathogen testing will be sent on the day of collection to the central laboratory for testing. Details of the processing, handling and shipping are provided in the separate sample handling manual. The results of these tests will be sent back to sites in two stages.

The initial report will state if pathogen DNA has been detected or not.

If pathogen (bacterial or fungal) DNA is detected this will be sequenced and pathogen identification will be reported to sites.

Details of the reporting process are provided in the separate diagnostic reporting manual.

If any sample material still remains after analysis this will be transferred to the Imperial Tissue Bank for analysis in other ethically approved studies

#### **Incidental findings**

There will be no clinical testing of samples beyond those described above for PCR-based pathogen testing that will be fed back to clinical care teams. Similarly, there are no additional clinical examinations other than routine clinical examination as part of standard care. Therefore, there will be no incidental finding reported to the patient, their clinical care team or their GP.

#### 7. TREATMENTS IN GM-CSF TRIAL

#### Treatment arms

Eligible patients will be randomised to one of two treatment arms

GM-CSF (sargramostim) - 500µg (two vials) for patients ≥50kg, and 250µg (one vial) for patients <50kg, given subcutaneously once a day for 8 days.

or

Matching placebo - two vials for patients ≥50kg, and one vial for patients <50kg, given subcutaneously once a day for 8 days.

Sponsor: Imperial College London

Version 1.1 22-Aug-2023

# **Investigational Medicinal Product Details**

GM-CSF (sargramostim) for Injection drug product is a sterile, lyophilized white cake in a stoppered Type I, 5mL glass vial. Drug product comprises 250µg of active ingredient sargramostim (recombinant DNA human GM-CSF) with excipients Mannitol, Sucrose, and Tromethamine.

The matching placebo contains Mannitol, Sucrose, buffer and a hydrochloric acid solution in matching 5ml glass vials.

GM-CSF (sargramostim) is used to accelerate neutrophil recovery, decreasing infectious morbidity and mortality. The first marketing authorization was granted in 1991. The six approved indications for sargramostim are:

- To shorten time to neutrophil recovery and to reduce the incidence of severe, life-threatening, or fatal infections following induction chemotherapy in adult patients 55 years and older with acute myelogenous leukaemia.
- In adult patients with cancer undergoing autologous hematopoietic stem cell transplantation for the mobilization of hematopoietic progenitor cells into peripheral blood for collection by leukapheresis.
- For acceleration of myeloid reconstitution following autologous peripheral blood progenitor cell or bone marrow transplantation in adult and paediatric patients 2 years of age and older with non-Hodgkin's lymphoma, acute lymphoblastic leukaemia, and Hodgkin's lymphoma.
- For the acceleration of myeloid reconstitution following allogeneic BMT in adult and paediatric
  patients 2 years of age and older undergoing allogeneic BMT from human leukocyte antigen
  (HLA)-matched related donors.
- For treatment of adult and paediatric patients 2 years and older who have undergone allogeneic or autologous BMT in whom neutrophil recovery is delayed or failed.
- To increase survival in adult and paediatric patients from birth to 17 years of age acutely exposed to myelosuppressive doses of radiation (hematopoietic syndrome of acute radiation syndrome.

It is not currently licensed for use in any indication in the UK. The active drug and placebo have been provided by Partner Therapeutics

The trial is being carried out under a Clinical Trial Authorisation (CTA) from the MHRA. The drug is therefore only to be used by the named investigators, for the participants specified in this protocol, and within the trial.

The Investigator Brochure (IB) is used for drug safety and other reference in this trial.

# Labelling and Packaging

Partner Therapeutics will be responsible for assuring that the quality of all IMPs are adequate for the duration of the trial and are in compliance with the Good Manufacturing Practice (GMP) standards.

Sargramostim (GM-CSF) and matched placebo will be imported from the USA. All drugs will be packaged, labelled and QP released according to the MHRA requirements and distributed to sites by Victoria Pharmaceuticals, Belfast. The Trial Co-ordination Centre will keep accurate records of supply to trial centres and destruction of unused IMP at the end of the trial.

Sponsor: Imperial College London

Version 1.1 22-Aug-2023

# Storage and Dispensing

The IMP will be delivered to the pharmacy at each participating site. Once received at site the IMP will be refrigerated and stored between  $2-8^{\circ}$ C. The pharmacy will then dispense the IMP to the ICU where this will be refrigerated until required. It is the responsibility of the site to ensure that accurate dispensing, prescriptions and returned records of the IMPs are maintained. The Study Coordination Centre will track supplies of IMPs via information from Victoria Pharmaceuticals and site IMP tracking documents. At the completion of the trial, the Trial Coordination Centre, via the monitor, will ensure the destruction of all returned dispensed IMPs (after close-out and before archiving). An IMP Management Plan will be generated to manage all aspects of IMP order, delivery, use and destruction during the course of the trial.

### **Accountability**

Site pharmacies will be responsible for recording IMPs dispensed to the ICU. Preparation of all drug infusions will be recorded on the Drug Accountability Form and drug administration on the patient's prescription chart. The Trial Coordination Centre will provide sites with an Inventory Log to keep track of all IMP vials, whether infused, opened but not infused or unused. At the end of the study any remaining unused drug will be returned to the hospital pharmacy for recording.

# **Drug interactions / Precautions / Contraindications**

Do not administer sargramostim (GM-CSF) to patients with a history of serious allergic reactions, including anaphylaxis, to human GM-CSF such as sargramostim, yeast-derived products, or any component of the product.

Sargramostim (GM-CSF) should be permanently discontinued if the total WBC count exceeds 50  $\times 10^9$  /L or if a serious allergic or anaphylactic reaction occurs.

#### Overdose of IMP

There is no clinical experience with sargramostim overdose. No specific antidote or detoxification measures can be recommended to date. If accidental overdose is suspected, the patient should be treated symptomatically.

#### **Dose Modifications for Toxicity**

In case of overdosage, discontinue sargramostim and monitor the patient for WBC increase and respiratory symptoms.

# Study drug administration

Lyophilised drug product should be reconstituted with 1mL of Sterile or Bacteriostatic Water for Injection for a 250 µg sargramostim/mL solution for subcutaneous injection. Full details will be provided in a separate administration guide.

#### Permanent Discontinuation of Study Treatment and Withdrawal from Study

# Permanent discontinuation of study treatment

Participants may discontinue study treatment for the following reasons:

Sponsor: Imperial College London

Version 1.1 22-Aug-2023

- At the request of the participant or their personal/professional legal representative
- Adverse Event/ Serious Adverse Event
- Allergic reaction to IMP
- If the investigator considers that a participant's health will be compromised due to adverse events or concomitant illness that develop after entering the study.

# Withdrawal from Study

Withdrawal from the study refers to discontinuation of study treatment and study procedures and can occur for the following reasons:

- Participant decision or their personal/professional legal representative
- Loss to follow-up

# **Procedures for Withdrawal from Study**

Patients will be free to withdraw at any time. If the patient (or their personal/professional legal representative) wishes to withdraw from the study during the treatment period the treating physician will no longer follow the trial protocol and the study drug will be stopped. If the participant withdraws from the study this will be documented in the eCRF and medical records.

The patient will be able to either withdraw completely from the trial or from certain elements. Further follow-up visits as part of the clinical trial will cease. However, the participant will be asked if data collection through data linkage of routinely collected data, including long-term follow-up can continue.

Participants will be asked if previously collected, stored blood samples can be used for further analyses or if they would prefer their samples to be destroyed.

Already collected data will not be deleted as these will include important safety information which would be processed as part of a legitimate interest.

### 8. PHARMACOVIGILANCE

# Adverse Event (AE)

An AE is any untoward medical occurrence in a patient or clinical trial participant administered a trial intervention / medicinal product and which does not necessarily have a causal relationship with this intervention / treatment. An AE can therefore be any unfavourable and unintended sign (including an abnormal laboratory finding), symptom, or disease temporally associated with the use of the trial medication, whether or not considered related to the IMP.

# Adverse Reaction (AR)

All untoward and unintended responses to an IMP related to any dose administered. All AEs judged by either the reporting investigator or the sponsor as having reasonable causal relationship to a medicinal product qualify as adverse reactions (ARs). The expression reasonable causal relationship means to convey in general that there is evidence or argument to suggest a causal relationship.

Sponsor: Imperial College London

Version 1.1 22-Aug-2023

# **Unexpected Adverse Reaction**

An AR, the nature or severity of which is not consistent with the applicable product information as set out in the Reference Safety Information (RSI) (in the investigator's brochure for an unapproved investigational product or summary of product characteristics (SmPC) for an authorised product).

When the outcome of the adverse reaction is not consistent with the applicable product information this adverse reaction should be considered as unexpected. Side effects documented in the RSI section of the SmPC/IB which occur in a more severe form than anticipated are also considered to be unexpected.

Expectedness assessment will be performed by the Sponsor or person delegated by the Sponsor to assess expectedness. This is delegated to the local site PI.

# Causality

The assignment of causality for adverse events should be made by the investigator responsible for the care of the participant using the definitions in the table below.

If any doubt about the causality exists the local investigator should inform the study coordination centre who will notify the Chief Investigator. The pharmaceutical companies and/or other clinicians may be asked to advise in some cases.

In the case of discrepant views on causality between the investigator and others, all parties will discuss the case. In the event that no agreement is made, the MHRA will be informed of both points of view.

Unrelated: No evidence of any causal relationship

*Unlikely:* There is little evidence to suggest there is a causal relationship (e.g. the event did not occur within a reasonable time after administration of the trial medication). There is another reasonable explanation for the event (e.g. the patient's clinical condition, other concomitant treatment).

*Possible:* There is some evidence to suggest a causal relationship (e.g. because the event occurs within a reasonable time after administration of the trial medication). However, the influence of other factors may have contributed to the event (e.g. the patient's clinical condition, other concomitant treatments).

*Probable:* There is evidence to suggest a causal relationship and the influence of other factors is unlikely.

*Definite:* There is clear evidence to suggest a causal relationship and other possible contributing factors can be ruled out.

# **Severity of Adverse Events**

Mild: Awareness of event but easily tolerated

Moderate: Discomfort enough to cause some interference with usual activity

Severe: Inability to carry out usual activity

Sponsor: Imperial College London

Version 1.1 22-Aug-2023

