### Additional inclusion criteria for GM-CSF trial only (can be after initial trial entry):

- Intubated and mechanically ventilated and expected to continue for another 24 hours
- Or requiring two organ support (i.e. vasopressors or renal replacement therapy)
- An absolute lymphocyte count < 1.2 x10^9/L on two consecutive calendar days at least 12 hours apart, with no values >1.2 x10^9/L in between.

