# **Adverse Event recording**

As this is a trial is conducted in critically ill patients with life-threatening sepsis then adverse events are expected to occur regularly in most, if not all, patients. Therefore, unless an adverse event is assessed to meet Serious Adverse Event criteria, these adverse events will not be reported in the case report form and simply noted in the patient's local medical record.

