# Reporting of SAEs

As the primary outcome of the trial includes mortality, then death does not require reporting as an SAE unless, in the opinion of the local PI, the death was attributable to a study intervention / IMP or the trial protocol.

Similarly, the secondary outcomes have been selected to capture the most commonly occurring safety events in critically ill patients (e.g. organ failure and support, and new infection, including Confidential 36

Sponsor: Imperial College London

Version 1.1 22-Aug-2023

Clostridium Difficile infection). Therefore, any events that are captured as an outcome in the eCRF do not require reporting as an SAE unless in the opinion of the local PI the event was attributable to a study intervention / IMP or the trial protocol.

Rapid reporting of all SAEs i.e. within 24 hours, occurring during the patient's ICU stay up to a maximum of 28 days must be performed as detailed in the study-specific safety reporting instructions.

Active monitoring of participants after discharge from ICU or after 28 days is not required, but if the investigator becomes aware of safety information that appears to be drug or trial related, involving a participant who participated in the study, even after an individual participant has completed the study, this should be reported to the Sponsor.

All SAEs will be reviewed by the Chief Investigator or a designated medically qualified representative to confirm expectedness and causality.

Reporting of SAEs and review by the CI will be via the trial data collection system (CRF/eCRF)

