### Analysis of secondary outcomes

Outcomes expressed as incidences or incidence rates will be examined using a suitable mixed effects regression model such as logistic, Poisson or negative binomial.

Outcomes where it is important to account for competing events such as death, or where the interest is in the timing or duration of the event, will be analysed as time-to-event or time-to-recovery data as appropriate, using sub-distribution hazard models(50) to account for the dependent competing risk of censoring when subjects transition to a less favourable clinical state (e.g. death).

All serious adverse events will be tabulated by arm and severity, displaying the number of participants with at least one adverse event and the number of adverse events. We will also calculate odds ratios and incidence rate ratios and their 95% CIs for binary and count SAE outcomes (including 1-year mortality) at SOC level using mixed effects logistic regression and Poisson, negative Binomial model or similar models for count data as appropriate.

Antibiotic use, quality of Life (EQ-5D-5L) and cognitive function (MoCA-Blind) will be summarised by arm (mean, standard deviation and 95% CI) and analysed using univariate linear mixed models.

All models used to analyse secondary outcomes will include the same adjusting variables as the corresponding primary analyses.

A detailed statistical analysis plan will be written prior to first data extraction from the database and will detail all analysis models and model checks to be performed.

Sponsor: Imperial College London

Version 1.1 22-Aug-2023

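### The only severity scale for adverse events rests on awareness, discomfort and usual activity, so it fits ICU patients poorly and weakens the severity split of the planned SAE table

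*Protocol*

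**What the plan says.** Protocol section 8, Severity of Adverse Events, defines three grades:

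- "Mild: Awareness of event but easily tolerated"
- "Moderate: Discomfort enough to cause some interference with usual activity"
- "Severe: Inability to carry out usual activity"

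Nothing in the protocol adapts these grades to sedated, ventilated or organ-supported patients.

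Other parts of the protocol decide which events are graded, and in whom:

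- Adverse Event recording: "unless an adverse event is assessed to meet Serious Adverse Event criteria, these adverse events will not be reported in the case report form".
- Reporting of SAEs: the reporting duty covers events "occurring during the patient's ICU stay up to a maximum of 28 days". Deaths, and events already captured as outcomes (organ failure and support, new infection), are exempt unless the local investigator attributes them to an intervention, the study drug or the protocol.
- GM-CSF inclusion criteria, section 5: "Intubated and mechanically ventilated and expected to continue for another 24 hours", or a need for two-organ support.

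The grade is used in section 9, Analysis of secondary outcomes: "All serious adverse events will be tabulated by arm and severity". The same paragraph plans odds ratios and incidence rate ratios by system organ class.

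**The concern.** A severity grade should separate the events that are recorded, and two sites should grade the same event alike. This scale has difficulty with both.

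First, its anchors presuppose a patient who is aware, can report discomfort and has usual activities to lose. Many participants will have none of these when the event starts. Does a ventilated patient's arrhythmia then count as severe because the patient cannot carry out usual activity, or is the scale not applicable because that was already so? The text does not say.

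Second, the scale separates events mainly at its lower end, while the case report form keeps only events at the upper end. An event that threatens life and one that merely prolongs the hospital stay can both receive the top grade, even in an awake patient.

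At stake is the severity column of a pre-specified safety table. The diagnostic and fluid comparisons are open-label, so a grade that needs an improvised rule could also be influenced by knowledge of the allocation. The Chief Investigator's review of SAEs is said to confirm expectedness and causality. Severity is not named, so no stated central check would bring the grades into line.

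**Working it through.** The protocol gives no figure for the distribution of severity grades, so there is none to reproduce. The check compares the scale with the patients and events to which it applies.

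**Step 1: anchors.** Mild uses awareness and tolerance. Moderate uses discomfort and interference with usual activity. Severe uses loss of usual activity. None refers to the patient's state before the event, to treatment needed, or to threat to life.

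**Step 2: events graded in the case report form.** Only events meeting the SAE definition are kept: death (mostly exempt from reporting), life-threatening events, hospitalisation or its prolongation, disability, congenital abnormality, and other events judged important. The scale has no step within that range above loss of usual activity.

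**Step 3: patients in the reporting window.** Table 2 of the protocol (standard-care arm) gives these anticipated proportions:

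| Day | ICU with support (s) | Hospital without support (h) | s / (s + h) |
|---|---|---|---|
| 0 | 0.85 | 0.15 | 0.85 |
| 7 | 0.41 | 0.48 | 0.41 / 0.89 = 0.46 |
| 14 | 0.29 | 0.32 | 0.29 / 0.61 = 0.48 |
| 28 | 0.14 | 0.17 | 0.14 / 0.31 = 0.45 |

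Patient-days over days 0 to 28, by the trapezoid rule (assumption: linear change between the tabulated days):

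- Supported: 7 × (0.85 + 0.41)/2 + 7 × (0.41 + 0.29)/2 + 14 × (0.29 + 0.14)/2 = 4.41 + 2.45 + 3.01 = 9.87 days per patient.
- Unsupported in hospital: 7 × (0.15 + 0.48)/2 + 7 × (0.48 + 0.32)/2 + 14 × (0.32 + 0.17)/2 = 2.205 + 2.80 + 3.43 = 8.435 days per patient.
- Supported share of hospital days: 9.87 / (9.87 + 8.435) = 0.54.

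The SAE window is the ICU stay, and some of the unsupported days are ward days outside it. The supported share of ICU days therefore lies between 54% (if every unsupported day is in ICU) and 100% (if every one is on the ward). Most of the window concerns organ-supported patients.

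In the GM-CSF trial, all 1300 planned participants meet the ventilation or two-organ-support criterion at entry.

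**Step 4: what uses the grade.** The SAE table by arm and severity does. The participant and event counts by arm, the ratios by system organ class, and the primary clinical-state analysis do not.

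**Limit of the check.** Table 2 counts patients by state, not SAEs, and organ support is wider than sedation or ventilation. The figures show how much of the window the scale fits badly. They do not give the proportion of SAEs that would be graded Severe.

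**The case against.** The case against acting has several parts.

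- **A reader might infer that nearly every SAE will be graded Severe and that the table carries no information.** The documents do not support this. The scale grades the event, so it can be read as interference caused by the event. For a patient with no usual activity it is undefined, not automatically Severe. The lowest grade does not mention activity, and 15% of patients are expected to be unsupported at day 0. Inconsistent grading is as plausible as a single filled row.
- **A reader might infer that the scale undermines expectedness and produces false SUSARs and needless unblinding.** This is not supported either. Under Unexpected Adverse Reaction, listed effects "which occur in a more severe form than anticipated are also considered to be unexpected", but the comparison is with the Reference Safety Information and does not invoke the three grades. A reaction must also be serious before it can become a SUSAR, so a mild, non-serious one cannot, however it is graded.
- **Serious events would cluster at the top of most scales.** This has force, and it reduces what is lost. It is also a reason to have a scale that separates serious events.
- **Harm is visible elsewhere.** This stands. The Data Monitoring Committee sees unblinded data. Death, clinical state and durations of organ support are measured directly.
- **Grading guidance may sit in the safety reporting instructions or the eCRF completion guide, which the protocol cites.** That is possible, and neither is shown. The protocol's own definitions would still need to agree with any such guidance. An analysis plan cannot recover a distinction that sites did not record on a common basis.

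**Conclusion.** The point holds in a limited form. The protocol's only severity scale uses anchors that many participants lack at the onset of an event, and it has no grade that separates life-threatening events from other serious ones. The severity split of the SAE table will therefore discriminate poorly or be graded inconsistently across about 60 sites.

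The size of the effect on the table cannot be computed. The scale fits badly for 85% of patients at day 0, for somewhere between 54% and 100% of ICU days to day 28, and for every GM-CSF participant at entry. These figures assume that the Table 2 proportions hold, that change between its time points is linear, and that organ support is a fair, if broad, marker of patients without usual activity.

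Sample size, power, the primary analysis, SAE counts by arm, the ratios by system organ class and the expectedness test are unaffected. This is a minor correction to reporting quality.

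**What to change.** Rewrite the definitions under Severity of Adverse Events so that each grade describes the event's own intensity and the change it causes from the patient's state immediately before it. One workable basis is the level of new intervention that the event required, with life-threatening as a separate grade. State that this grade fills the severity column of the SAE table in section 9, and bring the eCRF completion guide and safety reporting instructions into line.

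Keep the definitions compatible with Reporting of SAEs. Deaths and organ-support outcomes are exempt there unless attributed to an intervention, the study drug or the protocol. A fatal grade would therefore be mostly empty, and a grade defined only by new organ support would largely repeat outcomes collected elsewhere.

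The cost is one paragraph in the protocol, one eCRF list, brief site retraining, and regrading from the narratives of any SAEs already entered.
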